10.6 Progressive Disease

Natural progression or deterioration of the malignancy under study (including new sites of metastasis and death due to disease progression) should be recorded as part of the efficacy evaluation and should not be reported as AEs or SAEs.

Signs and symptoms clearly associated with the disease under study should NOT be reported as AEs unless they are any one of the following:

- Newly emergent (i.e., not previously observed in the subject).
- Judged by the investigator to be unusually severe or accelerated.
- Judged by the investigator to represent exacerbation of disease-related signs and symptoms to be caused directly by the study drug.

If there is reasonable uncertainty about an AE being caused by disease progression, it should be reported as an AE or SAE as appropriate.

10.7 Death on Study

If a patient dies while on study, permission for autopsy will be sought by the treating doctor. This information, when available, will be used in correlation with the clinical data.

10.8 Other Reportable Information

Certain information will be considered as SAEs for regulatory reporting purposes, and must be recorded, reported, and followed up as indicated for an SAE. This includes exposure to the test medication in the following:

- Pregnancy. If a pregnancy is confirmed, use of the test article must be discontinued immediately.
- Lactation.
- Overdose.
- Inadvertent or accidental exposure

10.9 Pregnancy Guidelines

During the course of the trial, all female patients of childbearing potential should be instructed to contact the treating physician immediately if they suspect they might have conceived a child. In addition, a missed or late menstrual period should be reported to the treating physician. If a female patient, or an investigator, suspects a pregnancy prior to administration of study drugs, the study drugs must be withheld until the results of a pregnancy test are available. If pregnancy is confirmed the patient must not receive study medications and must be withdrawn from the study. All supporters of the study will be informed if a pregnancy occurs.

Throughout the entire pregnancy, additional contact should be made with the patient and in some cases with the healthcare provider, to identify spontaneous abortions and elective terminations, as well as any medical reasons for elective termination. In addition, the study investigator should include perinatal and neonatal outcome. Infants should be followed for a minimum of 8 weeks.

If a male patient is suspected of having fathered a child while on study drugs, the pregnant female partner must be notified and counseled regarding the possible risk to the fetus. In addition, the treating physician must follow the course of the pregnancy, including prenatal and neonatal outcome. Infants should be followed for a minimum of 8 weeks.

All serious adverse event reports relating to the pregnancy, including spontaneous abortion, elective abortion and congenital anomalies, should be forwarded to the FDA and a copy sent to all supporters.

Any pregnancy that occurs during study participation should be reported. To ensure patient safety each pregnancy must also be reported to [name], the sponsor-investigator within 24 hours of learning of its occurrence. If the pregnancy is associated with a SAE then the pregnancy should be reported to BI Unique Entry Point within ten (10) calendar days upon receipt of the initial and/or

follow-up information. The pregnancy should be followed up to determine outcome, including spontaneous or voluntary termination, details of birth, and the presence or absence of any birth defects, congenital abnormalities or maternal and newborn complications.

10.10 Recording Adverse Events

Classification of Adverse Events

****AEs that do not meet any of the criteria for serious should be regarded as non-serious AEs.** The terms “severe” and “serious” are not synonymous.

Severity (or intensity) refers to the grade of a specific adverse event (e.g., mild; moderate; or severe).

Ex. A **severe** rash is not likely to be an **SAE**. Likewise, a **severe** headache is not necessarily an **SAE**. However, **mild** chest pain may result in a day’s hospitalization and thus is an **SAE**.

“Serious” is a regulatory definition (see above) and is based on subject or event outcome or action criteria usually associated with events that pose a threat to a subject’s life or functioning. Seriousness (not severity) serves as the guide for defining regulatory reporting obligations from the Sponsor to applicable regulatory authorities. Severity and seriousness should be independently assessed when recording AEs and SAEs on the CRF.

Collection of complete information concerning SAEs is extremely important. Full descriptions of each event will be followed. Thus, follow-up information which becomes available as the SAE evolves, as well as supporting documentation (e.g., hospital discharge summaries and autopsy reports), should be collected subsequently, if not available at the time of the initial report, and immediately sent using the same procedure as the initial SAE report.

The investigator must categorize the severity of each adverse event according to the following guidelines:

Criteria:

NCI toxicity criteria will be followed. Special attention will be paid to gastrointestinal, non-gastrointestinal perforation, leakage, fistula formation, abscess, and elevated transaminases.

Mild:	Grade I NCI Common Toxicity
Moderate:	Grade II NCI Common Toxicity
Moderately:	Severe: Grade III Common Toxicity
Severe:	Grade IV NCI Common Toxicity
Death:	Grade V NCI Common Toxicity

If the event is not found in the NCI Common Toxicity table, the adverse event will be scored using 5 grades:

Grade 1	Causing no limitation of usual activities
Grade 2	Causing some limitation of usual activities
Grade 3	Causing some inability to carry out usual activities
Grade 4	Causing life-threatening or disabling toxicity
Grade 5	Causing death

NCI Common Toxicity for Adverse Event Grading (Severity) Chart v4.0

Grade	Severity (Intensity)	Alternative Description
1	Mild; asymptomatic or mild symptoms; clinical or diagnostic observations only; intervention not indicated.	Transient or mild discomfort (< 48 hours); no interference with the subject's daily activities; no medical intervention/therapy required
2	Moderate; minimal, local or noninvasive intervention indicated; limiting age-appropriate instrumental ADL*	Mild to moderate interference with the subject's daily activities; no or minimal medical intervention/therapy required
3	Severe or medically significant but not immediately life-threatening; hospitalization or prolongation of hospitalization indicated; disabling; limiting self-care ADL**	Considerable interference with the subject's daily activities; medical intervention/therapy required; hospitalization possible
4	Life-threatening consequences; urgent intervention indicated.	Extreme limitation in activity; significant medical intervention/therapy required, hospitalization probable
5	Death related to AE	Death related to AE

Causal relationship of adverse event

Medical judgment should be used to determine the relationship, considering all relevant factors, including pattern of reaction, temporal relationship, de-challenge or re-challenge, confounding factors such as concomitant medication, concomitant diseases and relevant history. Assessment of causal relationship must be recorded for each adverse event.

Causality will be reported as either “Yes” or “No”.

Yes: There is a reasonable causal relationship between the investigational product administered and the AE.

No: There is no reasonable causal relationship between the investigational product administered and the AE.

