10.3.11 **Overdose** is defined as the accidental or intentional ingestion of any dose of a product that is considered both excessive and medically important. An overdose is defined as a dose increase of Nintedanib other than one prescribed by a health care professional or recommended by this protocol, whether accidental or intentional. For reporting purposes overdose does not need to be reported to Boehringer Ingelheim unless there is an SAE associated with the overdose. An overdose itself does not meet any criteria for reporting to BI (Safety) as an AE/SAE. If an SAE occurs due to overdose, the SAE should be reported and the information should be reported and the information should be reflected in the administration section of the SAE form.

10.3.12 A **pre-existing condition** is one that is present at the start of the study, and should be recorded as an adverse event if the frequency, intensity, or the character of the condition worsens during the study period.

10.3.13 **Seriousness** is a regulatory definition and is based on patient or event outcome or action criteria usually associated with events that pose a threat to a patient's life or functioning. Seriousness (not severity) serves as the guide for defining regulatory obligations from the Sponsor to applicable regulatory authorities.

10.3.14 **Severity** (or intensity) refers to the grade of a specific AE (e.g., mild (grade 1); moderate (grade 2); or severe (grade 3) myocardial infarction); see table for further details.

***Severity and seriousness should be independently assessed when recoding AEs and SAEs on the CRF.*

10.3.15 **Non-Serious AEs** are any events that do not meet any of the criteria for Serious.

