suspended until all patients have been followed for at least 6 months or until at least 4 patients (15%) are found progression-free at 6 months. If 3 or less of the patients are progression-free at 6 months, the therapy will be deemed ineffective. If 4 or more of the patients are progression-free at 6 months, another 29 patients will be accrued. If 10 or less of the 56 patients are progression-free at 6 months, the therapy will be deemed ineffective. If at least 11 patients (20%) are progression-free at 6 months, the therapy will be deemed effective and worthy of further research. These stopping rules are illustrated in the table below.

Stage	Sample Size	Minimum number of patients who must be progression-free at 6-months for therapy to be considered effective
1	27	4 (15%)
2	56	11 (20%)

This design has a one-sided Type I error of 0.10, a power of 0.90. The probabilities of early termination given the null and the alternative are 0.54 and 0.04, respectively. If exactly 11 responses are observed, the exact 80% confidence interval will be [0.13, 0.28]. If even one patient drops out or is lost-to-follow-up before progression, then we will not be able to tabulate the number of patients who are progression-free at 6 months. In this case, we will calculate the Kaplan-Meier curve and focus on the probability of surviving to 6 months as calculated by the Kaplan-Meier method. We will call this trial a success only if the lower 10% confidence bound of this probability is greater than 0.13.

Statistical Analysis of Secondary Aims

Secondary Aim 1 is to determine the proportion of patient who has an objective tumor response (complete or partial). To address this aim all responses will be tabulated: complete response, partial response, stable disease, progressive disease.

Secondary Aim 2 is to determine the frequency and severity of adverse events. To address this aim, all toxicities will be tabulated by type and grade.

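### Section 10 puts the words severe and disabling at grade 3 in one place and grade 4 in another, so the grade 3/4 split can be wrong for events recorded by word or not listed in CTCAE

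*Combined protocol and SAP*

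**What the plan says.** Severity of adverse events is a secondary objective (1.2.3) and a secondary endpoint (11.2.2.2), assessed by NCI criteria; 1.2.3 names version 4. The introduction to section 10 adopts CTCAE v4.0 for both AE and SAE reporting. Under Secondary Aim 2 in section 11, "all toxicities will be tabulated by type and grade".

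Section 10 then describes severity in four places:

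- **10.3.14** gives the example "mild (grade 1); moderate (grade 2); or severe (grade 3) myocardial infarction".
- **10.10, word list.** The grade III line ends "Severe: Grade III Common Toxicity"; with the word before it, the label is moderately severe. The next line gives *severe* as "Grade IV NCI Common Toxicity".
- **10.10, scale for events not found in the NCI table.** Grade 4 is "Causing life-threatening or disabling toxicity".
- **10.10, v4.0 chart.** Grade 3 is "Severe or medically significant but not immediately life-threatening; hospitalization or prolongation of hospitalization indicated; disabling; limiting self-care ADL". Grade 4 is reserved for life-threatening consequences.

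**The concern.** The word list is introduced as something the investigator must use, so it is an operative instruction. It conflicts with the definition in 10.3.14 and with the chart that follows it. The scale for unlisted events and the chart are both general, with no event-specific terms. They are printed one after the other, and they place a disabling event at different grades.

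The Aim 2 table is by grade. If the same event can be entered as grade 3 under one part of section 10 and grade 4 under another, the split between those two rows partly reflects which part was read. This is a multi-center, single-arm study, so no control arm would show or offset a difference in grading practice.

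**Working it through.** The check is a comparison of text. The plan states no figure on this point, so there is none to reproduce.

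**Step 1. Set the four descriptions side by side.**

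| Source | Grade given to *severe* | Grade given to *disabling* |
|---|---|---|
| 10.3.14 | 3 ("severe (grade 3) myocardial infarction") | not mentioned |
| 10.10 word list | 4 (grade 3 is moderately severe) | not mentioned |
| 10.10 scale for unlisted events | not used | 4 |
| 10.10 v4.0 chart | 3 ("Severe or medically significant but not immediately life-threatening") | 3 |

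*Severe* is grade 4 once and grade 3 twice. *Disabling* is grade 4 once and grade 3 once.

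**Step 2. Ask which scale governs.** Objective 1.2.3, the introduction to section 10 and the opening of the criteria in 10.10 all point to the NCI criteria, and the first two name version 4. For an event with its own CTCAE term, the numeric grade comes from CTCAE. The word attached to that grade does not alter it.

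**Step 3. Find the routes by which the conflict can still reach the Aim 2 table.**

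- *Recording by word.* Section 10.11 asks for the intensity of every adverse event. Section 10.10 equates intensity with grade and illustrates it with words. An entry of *severe* becomes grade 4 under the word list and grade 3 under 10.3.14 or the chart.
- *Unlisted events.* A disabling event that is not life-threatening is grade 4 on the scale for unlisted events and grade 3 on the chart. Section 10.11 refers the severity item of an SAE report to a chart, and the only item in 10.10 with that title is the v4.0 chart. One unlisted SAE could therefore carry grade 4 under one instruction and grade 3 under the other.

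**Step 4. Work out what moves and what does not.** Let n3 and n4 be the grade 3 and grade 4 counts, and let k events move from 3 to 4. The rows become n3 − k and n4 + k. Their sum is (n3 − k) + (n4 + k) = n3 + n4, so the count at grade 3 or 4, and with it the count at grade 3 or higher, is unchanged for any k. Section 6.4 names grades 3 and 4 together with one set of actions, so a move between them does not change whether it applies.

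**Step 5. Check the grade 2/3 boundary.** Match like with like. Grade 2 on the scale for unlisted events (some limitation of activities) sits beside chart grade 2 (instrumental activities limited; mild to moderate interference). Grade 3 on that scale (some inability) sits beside chart grade 3 (considerable interference). The wording differs, but the text does not force any event to be 2 on one and 3 on the other.

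**The case against.** The strongest reply is that the endpoint is a number. CTCAE v4.0 is named repeatedly, Aim 2 tabulates by grade, and the word list only attaches labels to NCI grades, so it is not a rival scale. The scale for unlisted events is not a site's choice either, because it is confined to events missing from the NCI table. The SAE severity item points to a chart whose first column is the numeric grade, and Table 8 in 10.14 provides a dedicated form for toxicity reporting. No section says that words are later converted to grades. The table is descriptive, and section 11 has no test or decision rule based on grade.

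Most of this stands. It disposes of a stronger reading that a reader might take from section 10: that the severity endpoint as a whole depends on which scale a site uses. For listed events graded by number, it does not.

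The reply does not remove the contradiction. The conflicting word list is presented as mandatory, intensity is requested for every event, and nothing says when the chart applies in place of the scale for unlisted events.

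**Conclusion.** Minor, and wrong as written. Section 10.10 contradicts itself on *disabling*, and its word list contradicts both 10.3.14 and its own chart on *severe*. The consequence is limited to the grade 3 versus grade 4 split in the Aim 2 table, for the two kinds of event in Step 3. The first kind matters only if sites enter words that are later turned into grades, which the documents neither require nor rule out. The second matters only if such unlisted events occur.

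Two further inferences are tempting and are not supported:

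- *That the inconsistency changes treatment exposure through 6.4.* The demonstrated conflicts are all between grades 3 and 4, which 6.4 treats alike, and no grade 2/3 conflict is shown.
- *That the shift can be sized from the earlier randomized ovarian trial in 2.4, which reported grade 3 and grade 4 events in 54% and 7% of nintedanib patients.* Any share of grade 3 events moved to grade 4 would be invented. Many events in that trial were liver enzyme elevations (43%), and 6.2 describes hepatic grading by multiples of the upper limit of normal, which a verbal label cannot move.

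The size is therefore unknown. The primary endpoint is not touched.

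**What to change.** Make three edits to section 10:

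1. Delete the mild-to-severe word list in 10.10, or align its labels with the v4.0 chart and 10.3.14.
2. State in 10.10 and 10.11 that the numeric CTCAE v4.0 grade is recorded for every AE and SAE, so that the intensity and severity items are both numbers.
3. Replace the separate scale for unlisted events with the v4.0 chart already printed in 10.10, and say that the chart applies to any event without a specific CTCAE term.

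The cost is the removal or correction of two short lists and a clearer form instruction. No new data are collected. If any events have already been entered by word or graded on the separate scale, assign their numeric v4.0 grade from source before the Aim 2 table is produced.

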10.11 Procedures For Reporting

Reporting of Adverse Events:

Upon inclusion into a trial, the patient's condition is assessed (e.g., documentation of history/concomitant diagnoses and diseases), and relevant changes from baseline are noted subsequently.

All adverse events, serious and non-serious, occurring during the course of the clinical trial (i.e., from signing the informed consent onwards through the trial defined follow-up period) will be collected, documented and reported by the investigator. For each adverse event, the investigator will provide the onset date, end date, intensity, treatment required, outcome, seriousness, and action taken with the investigational drug. The investigator will determine the expectedness of the investigational drug to the AEs as defined in the Listed Adverse Events section of the Boehringer Ingelheim's Investigator Brochure for the Product.

Serious Adverse Events (SAEs) and unknown reactions or unexpected events that occur in the course of any patient's treatment on study or within 30 days following cessation of treatment should be reported to the Principal Investigator and the lead site/Sponsor ([name]/Duke University) within 24 hours of learning of the event. SAEs must be recorded using the Boehringer Ingelheim SAE Reporting Form, found in the Procedure Manual.

Additional information and/or corrections may be submitted as they are obtained. All SAEs must be followed through resolution or stabilization.

All adverse events, regardless of severity, and whether or not ascribed to the study drug administration, will be recorded in the appropriate section of the Case Report Form. Patients withdrawn from the study due to AEs will be followed by the Investigator until the outcome is determined and, when appropriate, additional written reports and documentation will be provided.

The DCI Safety Desk at Duke University should be contacted when reporting an SAE and should be faxed or emailed to the following:

DCI Safety at Duke University (on behalf of [name] [name])
[contact]
[contact]
Email: [contact]

If this person cannot be reached within 24 hours, the Principle Investigator and/or Chief Medical Officer should be contacted:

[name] [name]
Duke University Medical Center
[name]
[name]
[contact]
[contact]
[contact]

Minimum Criteria for Reporting:

Information for final description and evaluation of a case report may not be available with the required time frames for reporting. Nevertheless, for regulatory

purposes, initial report shall be submitted within the prescribed time as long as the following minimal requirements are met:

The ***initial*** report for each SAE should include at minimum the following information:

- Protocol # and title.
- Regulatory Seriousness criteria if applicable (i.e., death; life-threatening; hospitalization; etc.).
- Patient initials, study identification number, sex, and age.
- Date the event occurred (onset).
- Severity (intensity) - see chart.
- Description of the SAE.
- Dose level and cycle number at the time the SAE occurred.
- Description of the patient's condition.
- Indication whether the patient remains on study.
- Causality (relationship of the event to the study medication).

Follow-up information may include:

- Severity (intensity) - see chart.
- Duration of the event.
- Treatment and/or medication(s) given for the event, if any.
- Brief narrative summarizing the relevant details of the event.
- Action taken to study medication.
- Concomitant medications.
- Event outcome with dates should be communicated to the Duke as soon as possible.
- When applicable and requested, information from relevant hospital records (e.g., discharge summary, autopsy reports, etc.).

Upon receipt of the Serious Adverse Event Report Form by Duke, DCI Safety will:

- a. Notify [name] of the event via email and obtain an assessment for each event via the SAE Review Form.
- b. Fax the form to Boehringer Ingelheim Global Pharmacovigilance Center US (GPV Centre US) at [name]

All adverse events, regardless of severity, and whether or not ascribed to the study drug administration, will be recorded in the appropriate section of the Case Report Form. Patients withdrawn from the study due to AEs will be followed by the Investigator until the outcome is determined and, when appropriate, additional written reports and documentation will be provided.

10.12 Regulatory (Expedited) Reporting

As per 21 CFR 312.2(a), this study must be conducted under an IND. [name] [name] of Duke University Medical Center will be the sponsor-investigator for this study and will hold the IND. Thus, [name] will serve as both a principal investigator and the regulatory sponsor of this multi-center study.

Per 21 CFR 312.32(c), the sponsor will notify the FDA and all participating investigators in a written IND Safety Report of:

- (A) Any adverse event associated with the use of the drug
- (B) That is both serious and unexpected (see above for definitions).

- Each notification shall be made as soon as possible and in no event later than 15 calendar days after the sponsor's initial receipt of the information. Each written notification may be submitted on FDA Form 3500A (MedWatch form) or in a narrative format. In each written IND safety report, the sponsor shall identify all safety reports previously filed with the IND concerning a similar adverse experience, and shall analyze the significance of the adverse experience in light of the previous, similar reports.
- The sponsor shall also notify the FDA by telephone or by fax of any unexpected fatal or life-threatening experience associated with the use of the drug as soon as possible but no later than 7 calendar days after the sponsor's initial receipt of the information.
- Follow-up information to a safety report shall be submitted as soon as the relevant information is available.
- Additionally, adverse events will be reported to the FDA in an annual report according to annual report requirements. Events will be reviewed and reported to the Duke IRB according to local IRB guidelines.

